Men with progressive metastatic CRPC received 2 fractionated doses two weeks apart. Initially, 6 cohorts of 3–6 pts got 2 doses of ¹⁷⁷Lu–J591 2 wks apart (20 mCi/m², escalating to 45 mCi/m² x2). Subsequently, pts enrolled in 2 expansion cohorts at the recommended phase 2 doses (RP2D). Planar ¹⁷⁷Lu–J591 imaging was semi–quantitatively scored. The endpoints were PSA changes and survival (OS); as well as CTC count (CellSearch) changes in the expansion cohorts. 49 patients, with median age 74.1 years (range 55–95), median PSA of 44.9 ng/mL (1.9–766.5); 83.7% with bone, 61.2% with lymph node, 40.8% with visceral metastasis. 8.2% were CALGB (Halabi) low, 34.7% were intermediate, 57.1% were in high–risk group. RP2D’s of fractionated ¹⁷⁷Lu–J591 were 40 mCi/m² x2 or 45 mCi/m² x2 with option for GCSF. PSA changes for the low dose group were reported as 6.3% showing >50% PSA decline, 12.5% reporting >30% PSA decline, and 37.5% with any PSA decline. within RP2D group 21.2% showing >50% PSA decline, 42.4% reporting >30% PSA decline, and 66.7% with any PSA decline. The median overall survival for low dose group was 14.6 months and for RP2D group was 27.7 months. Accurate targeting of ¹⁷⁷Lu–J591 was seen in 79.6%. Patients with lower PSMA expression by imaging were less likely to respond (p=0.07). Of 25 with CTC counts, 14 declined, 8 stably favorable, and 3 increased. RP2D was associated with more PSA declines (p=0.036) and longer OS (p=0.004), even after controlling for CALGB prognostic grouping (adjusted HR 0.42 [95% CI 0.21, 0.84] p=0.01). Predictable, reversible myelosuppression was seen. 36 (73.5%) patients had grade 3/4 heme toxicities; 19 (57.6%) had Grade 4 heme toxicities in RP2D cohorts with 45.4% receiving prophylactic platelet transfusions (median 1, range 1–4) and 6 GCSF. 14 (28.6%) had infusion reactions (without pre–meds), with 1 patient having Grade 2 infusion reaction leading to withdrawing from the study prior to his 2nd dose. 5 (10.2%) had transient Gr 1/2 AST/ALT. This study concluded that fractionated ¹⁷⁷Lu–J591 is well tolerated with predictable, reversible myelosuppression and PSA and CTC declines. Additionally, with dose–fractionation, the cumulative dose MTD is 14–28% higher than single dose MTD with similar toxicity.

Table 1: Toxicities data from Phase 2 single dose ¹⁷⁷Lu–J591 Study and Phase 1 fractionated ¹⁷⁷Lu–J591 study:

| | Single Dose | Fractionated Dose |
|--|-------------|-------------------|
|--|-------------|-------------------|

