Taken together, with >250 patients treated on these sequential clinical trials, we have drawn the following conclusions: (i) there is a clear dose-response with more responses and longer survival at higher doses; (ii) there is clear dose-toxicity response in terms of myelosuppression (which is both predictable and reversible); (iii) dose-fractionation allows higher cumulative dose with comparatively less toxicity (including allowing concurrent chemotherapy); and (iv) without pre-selection for PSMA expression, approximately 90% have accurate tumor targeting, though the small minority with low/no PSMA expression by imaging have a lower likelihood of response. While ^{177}Lu -J591 mAb demonstrated significant efficacy, the major limitation in the optimization of therapeutic dose is the hematological toxicity (described in greater detail below).

With a single-dose, 70 mCi/m² of ^{177}Lu -J591 was the MTD, with dose-limiting myelosuppression in those receiving 75 mCi/m² (with 2 of 3 with dose-limiting hematologic toxicity)(28). In the phase II study, this was confirmed with 70 mCi/m² of ^{177}Lu -J591 being tolerable with reversible myelosuppression, but with a significant amount of manageable grade 4 myelosuppression (including approximately 40% platelet transfusion)(39).

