Men with progressive metastatic CRPC received 2 fractionated doses two weeks apart. Initially, 6 cohorts of 3–6 pts got 2 doses of ^{177}Lu -J591 2 weeks apart (20 mCi/m², escalating to 45 mCi/m² x2). Subsequently, pts enrolled in 2 expansion cohorts at the recommended phase 2 doses (RP2D). Planar ^{177}Lu -J591 imaging was semi-quantitatively scored. The endpoints were PSA changes and survival (OS); as well as CTC count (CellSearch) changes in the expansion cohorts. 49 patients, with median age 74.1 years (range 55–95), median PSA of 44.9 ng/mL (1.9–766.5); 83.7% with bone, 61.2% with lymph node, 40.8% with visceral metastasis. 8.2% were CALGB (Halabi) low, 34.7% were intermediate, 57.1% were in high-risk group. RP2D's of fractionated ^{177}Lu -J591 were 40 mCi/m² x2 or 45 mCi/m² x2 with option for GCSF. PSA changes for the low dose group were reported as 6.3% showing >50% PSA decline, 12.5% reporting >30% PSA decline, and 37.5% with any PSA decline. within RP2D group 21.2% showing >50% PSA decline, 42.4% reporting >30% PSA decline, and 66.7% with any PSA decline. The median overall survival for low dose group was 14.6 months and for RP2D group was 27.7 months. Accurate targeting of ^{177}Lu -J591 was seen in 79.6%. Patients with lower PSMA expression by imaging were less likely to respond (p=0.07). Of 25 with CTC counts, 14 declined, 8 stably favorable, and 3 increased. RP2D was associated with more PSA declines (p=0.036) and longer OS (p=0.004), even after controlling for CALGB prognostic grouping (adjusted HR 0.42 [95% CI 0.21, 0.84] p=0.01). Predictable, reversible myelosuppression was seen. 36 (73.5%) patients had grade 3/4 heme toxicities; 19 (57.6%) had Grade 4 heme toxicities in RP2D cohorts with 45.4% receiving prophylactic platelet transfusions (median 1, range 1–4) and 6 GCSF. 14 (28.6%) had infusion reactions (without pre-meds), with 1 patient having Grade 2 infusion reaction leading to withdrawing from the study prior to his 2nd dose. 5 (10.2%) had transient Gr 1/2 AST/ALT. This study concluded that fractionated ^{177}Lu -J591 is well tolerated with predictable, reversible myelosuppression and PSA and CTC declines. Additionally, with dose-fractionation, the cumulative dose MTD is 14–28% higher than single dose MTD with similar toxicity.

Table 11: Toxicities data from Phase 2 single dose ¹⁷⁷Lu–J591 Study and Phase 1 fractionated ¹⁷⁷Lu–J591 study:

| | Single Dose | | Fractionated Dose | | |

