4. OVERVIEW OF STUDY DESIGN AND METHODOLOGY

4.1 Study Design

This is an open-label, single-center Phase I dose-escalation study designed to determine the dose-limiting toxicity (DLT) and the maximum tolerated dose (MTD) of combination of ¹⁷⁷Lu-J591 and ¹⁷⁷Lu-PSMA-617 in a two-week dose-fractionation regimen. ¹⁷⁷Lu-J591 will be given at a moderate dose previously demonstrated to be safe x2 infusions two weeks apart. For ¹⁷⁷Lu-PSMA-617 the dose escalation will start at 3.7 GBq (100 mCi) and escalate in increments of 1.85 GBq (50 mCi) for each dose to a planned maximum of 9.25 GBq (250 mCi) x2 doses, 2 weeks apart. Should there be unacceptable toxicity at the initial dose level, we will de-escalate to dose level -1 (1.85 GBq / 50 mCi per dose). After the phase I study has established a MTD, the Phase II, single-arm trial will start.

Patients must have documented progressive metastatic CRPC disease based on Prostate Cancer Working Group 3 (PCWG3) criteria in order to be eligible for enrollment. Upon meeting the inclusion and exclusion criteria and signing the informed consent and HIPPA form, subjects will undergo the screening. As part of the screening, subjects will get a single dose of ⁶⁸Ga-PSMA-HBED-CC and will have a PET/CT. Nuclear Medicine physician(s) will review the PET/CT scans to document PSMA expression at tumor site(s).

Subjects will have Lutetium-177 Planar/SPECT Imaging on Day 8 (±1 day) after the first dose of ¹⁷⁷Lu-J591 + ¹⁷⁷Lu-PSMA-617. Optimal images will be performed on selected consenting subjects between the initial treatment visit #1 on Day 1 and Day 4 and prior to treatment visit #2 on D15 ±1. Subjects will be closely monitored for AEs (weekly x2 weeks, then every 2 weeks for one month, at 8 and 12 weeks, and then every 4 weeks for next 3 months).

Upon completion of investigational treatment with dose-fractionation regimen of the combination of ¹⁷⁷Lu-J591 + ¹⁷⁷Lu-PSMA-617, subjects will undergo ⁶⁸Ga-PSMA-HBED-CC injection and same day PET/CT at the end of study visit to document treatment response. Subsequently survival data and additional treatment(s) information will be captured from their routine Standard of care (SOC) visits.

Table 14: Phase I dose-escalation plan for combination of ¹⁷⁷Lu-J591 + ¹⁷⁷Lu-PSMA-617:

| ¹⁷⁷Lu–J591 + ¹⁷⁷Lu–PSMA–617: Dose escalation (per dose) | | |
|--|----------------------------------|----------------------------------|
| | ¹⁷⁷Lu–J591* | ¹⁷⁷Lu–PSMA–617 |

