Median bPFS, rPFS, and OS, including survival curves, will be estimated using Kaplan-Meier methodology. Greenwood's formula will be used to calculate 95% confidence intervals for the Kaplan-Meier estimates. Percent change in PSA from baseline will be described by mean/median and standard deviation/inter-quartile range, as appropriate, depending on the distribution of percent change from baseline. Modified RECIST response (i.e., CR, PR, and CR/PR proportions), CTC count response proportion, defined favorable LDH/CTC proportion, and associated 95% confidence intervals, will be estimated via binomial proportions.

All subjects will be offered optional but recommended baseline and subsequent ⁶⁸Ga-PSMA-HBED-CC PET/CT, and those treated with ¹⁷⁷Lu-labeled products will undergo Planar/SPECT imaging. We will analyze the data for associations with response to treatment as well as survival by chi-square tests/Fisher's exact tests and log-rank tests, respectively. For pre/post imaging comparisons, McNemar's chi-square test and paired t-tests/Wilcoxon signed-rank tests will be used, as appropriate. We plan to report data for each individual study as well as across the studies.

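### PSMA imaging is related to response and survival only by tests that need groups; where the reading is continuous or ordered, rank, trend and Cox analyses would use it better at no cost

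*Combined protocol and SAP*

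**What the plan says.** Section 10.8, under Analysis of Efficacy, covers the 68Ga-PSMA PET/CT and the 177Lu planar/SPECT data together. The imaging data will be analysed for "associations with response to treatment as well as survival by chi-square" or Fisher's exact tests (response) and log-rank tests (survival). For change between scans it adds that "McNemar's chi-square test and paired t-tests/Wilcoxon signed-rank tests will be used, as appropriate".

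No imaging variable, scale, cut-point or number of groups is given for this trial. Section 4.1 says only that nuclear medicine physicians review the screening PET/CT to document PSMA expression. Sections 10 and 12 name no rank, trend, logistic or Cox method for imaging against outcome. By contrast, Section 10.9 uses the same family of tests for calreticulin but names four categories.

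The background gives a direction. Section 2.7 says that "the small minority with low/no PSMA expression by imaging have a lower likelihood of response". In the group's earlier fractionated J591 study, planar "imaging was semi-quantitatively scored", and lower expression went with less response at p=0.07 (Sections 2.3.1.2 and 2.7). Section 1.3 lists PSMA-imaging disease assessment as an exploratory objective.

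**The concern.** Chi-square, Fisher and log-rank tests compare groups. A standardised uptake value would have to be cut first, and the plan does not say where. An ordered score needs no cut, but an unordered chi-square treats its levels as interchangeable and so ignores the expected direction (more uptake, more response).

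Two things are at stake, both modest. With at most 27 phase II patients there is little information to spare. And with no groups fixed in advance, a split could be chosen after the outcomes are seen. Section 10.8 also plans to report across studies, which is easier if each study keeps the reading on its own scale.

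**Working it through.** **What the plan's own figures give.** The documents state no effect size, significance level or power for the imaging associations, so there is no imaging figure to reproduce. The sample size comes from the Simon design in Section 12.2: continue with at least 7 of 16, declare activity with at least 13 of 27. Exact two-stage binomial sums give a one-sided error of 0.0979 at 35% and power of 0.9001 at 60%, which matches the stated 0.10 and 0.90. So n = 27 is taken as given. The overall ceiling of 57 treated patients is used as a second case.

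**Assumptions (not in the documents).** Uptake x is standard normal; two-sided 5%; logistic relation to response with odds ratio OR per SD; exponential survival with hazard ratio HR per SD; 50% response rate in the table below.

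**Response, n = 27 (2,000 simulated trials per row; power in %).**

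| OR per SD | Fisher, median split | Chi-square, median split | Mann-Whitney, full scale | Chi-square loss | Fisher loss |
|---|---|---|---|---|---|
| 1 (null) | 3.1 | 5.9 | 5.0 | – | – |
| 1.5 | 7.8 | 13.1 | 16.1 | 3.0 | 8.3 |
| 2 | 17.6 | 27.0 | 35.4 | 8.4 | 17.8 |
| 3 | 38.6 | 50.0 | 63.9 | 13.9 | 25.3 |
| 4 | 50.2 | 64.0 | 78.7 | 14.7 | 28.5 |

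With 60% response (the plan's alternative) and OR 2.2 to 5.0, the loss was about 10–19 points for chi-square and 16–30 for Fisher. The null row shows that Fisher rejects too rarely, so part of its gap is conservatism and not grouping. The chi-square gap cannot be explained that way.

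**If the reading is a four-level score and no cut is made.** Unordered four-group chi-square against a trend test, n = 27: 21.8% v 32.4% at OR 2 (10.6 points), 42.9% v 59.8% at OR 3 (16.9), 55.8% v 73.1% at OR 4 (17.3). At OR 1.5 the gap is 4.0 points (10.8% v 14.8%).

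**Survival, n = 27 (3,000 trials per row; log-rank on a median split v Cox score test on x).**

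| HR per SD | All events observed | About one third censored |
|---|---|---|
| 1.3 | 17.9 v 24.4 (6.5) | 12.4 v 17.2 (4.8) |
| 1.5 | 31.6 v 45.8 (14.3) | 24.8 v 34.5 (9.7) |
| 2 | 65.6 v 85.6 (20.0) | 52.1 v 70.8 (18.8) |
| 2.5 | 83.5 v 96.4 (12.9) | 69.4 v 88.6 (19.3) |

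**Analytic check.** A median split of a normal variable keeps a fraction 2/π of the information. If the full-scale test has power P, the grouped test has power Φ[(1.96 + z_P)·√(2/π) − 1.96]. For P = 0.70: (1.96 + 0.524) × 0.798 = 1.982, and Φ(0.022) = 0.51, a loss of 19 points. For P = 0.30: (1.96 − 0.524) × 0.798 = 1.146, and Φ(−0.814) = 0.21, a loss of 9 points.

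**At n = 57 the gap narrows when power is high.** Chi-square v Mann-Whitney: 53.5% v 64.8% at OR 2, 94.4% v 98.8% at OR 4. Log-rank v Cox, all events: 60.8% v 80.6% at HR 1.5, 95.0% v 99.4% at HR 2.

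**The case against.** The strongest reply is that nothing in the documents says the imaging reading in this trial is graded. Screening PET only documents expression, the semi-quantitative score belongs to an earlier study, and the sentence listing paired t and Wilcoxon tests begins with McNemar's test, which needs a categorical reading. That stands: the plan expects both kinds of data, and a graded measure is an inference. It does not remove the point. The paired t and Wilcoxon tests have no use unless some readings are quantitative or ordered, and for those no suitable test against outcome is named. If the reading is an ordered score, the loss from ignoring order remains.

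The second reply is that the objective is exploratory, that Section 12.1 plans no formal hypothesis testing in phase I, and that data will be reported across studies. This limits the importance of the point and is accepted.

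A reader might infer more than the documents support:

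- **A fixed loss at this trial's size, such as 15 to 25 points.** Any such figure depends on an assumed effect, cut and test. The tables above run from 3 to over 28 points, and the top of that range partly reflects Fisher's conservatism.
- **That a low-versus-other comparison is hopeless.** Section 2.7's roughly 90% targeting suggests about 3 of 27 low expressors, and 0/3 against 16/24 gives Fisher p=0.056. But the fractionated study reports 79.6% targeting, so 20.4% × 27 is about 5 or 6. Then 0/5 against 16/22 gives p=0.006.
- **That the earlier p=0.07 shows the cost of grouping.** The documents do not say which test or scale produced it.

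**Conclusion.** The point holds as a minor improvement to an exploratory analysis. Section 10.8 names only group-based tests for PSMA imaging against response and survival, defines no groups, and provides nothing that uses the order of a continuous or ordinal reading.

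Under the stated assumptions, a median split at n = 27 costs roughly 10–20 points for chi-square against a rank test over odds ratios of about 2 to 5 per SD. It costs more for Fisher, and about 5–20 points for log-rank against Cox. The cost is small when the effect is weak or power is already high. All of this rests on effect sizes that the documents do not give, a roughly monotone relation, a normally distributed reading, and imaging in all 27 patients. The last may not hold, because Section 10.8 calls the PSMA PET optional while Table 15 schedules it for everyone.

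The primary result, the decision rules and the secondary endpoints are not affected.

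**What to change.** In Section 10.8, replace the association sentence with text to this effect:

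- Where the imaging measure is continuous or ordered, its association with response (PSA decline of at least 30%) will be tested on its full scale: Wilcoxon rank-sum for a continuous measure, Cochran-Armitage trend test for an ordinal score.
- Its association with progression-free and overall survival will be tested by Cox regression with the measure as a continuous or ordinal term.
- Chi-square or Fisher tests are kept for readings that are truly categorical.
- Grouped tables and Kaplan-Meier curves are for display.

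This does not itself choose the reading. The team should name the scan and the summary measure before looking at outcomes.

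The change is a few lines of text and needs no further patients or scans. The downside is that the Cox and trend terms assume a roughly monotone effect, which the grouped displays can check.

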10.9 Calreticulin Expression on CTCs (immune measure)

We will analyze for associations between calreticulin expression as a categorical variable (membrane vs cytoplasmic vs mixed vs no expression) and response to treatment and survival using chi-square tests/Fisher's exact tests and log-rank tests, respectively. We plan to report data for each individual study as well as across PSMA studies.

10.10 Patient reported outcomes

Initial bone-targeted β -emitters were approved for the control of painful bone metastases. Radium-223 dichloride appears to be associated with improved/preserved patient reported outcomes as well. We will assess pain prior to and following treatment with the brief pain inventory (and will also collect pain medication data). We will assess global and prostate cancer specific patient reported outcomes with BPI-SF and FACT-P questionnaire. As with the other correlative studies, we will plan to report results for this individual study as well as across current and prior studies, particularly examining subjects that receive what we believe are efficacious doses.

11. DATA REPORTING / REGULATORY CONSIDERATIONS

11.1. Data Collection

The data collection plan for this study is to utilize REDCap to capture all treatment, toxicity, efficacy, and adverse event data for all enrolled patients.

11.1.1. REDCap

REDCap (Research Electronic Data Capture) is a free data management software system that is fully supported by the Weill-Cornell Medical Center CTSC. It is a tool for the creation of customized, secure data management systems that include Web-based data-entry forms, reporting tools, and a full array of security features including user and group based privileges, authentication using institution LDAP system, with a full audit trail of data manipulation and export procedures. REDCap is maintained on CTSC-owned servers that are backed up nightly and support encrypted (SSL-based) connections. Nationally, the software is developed, enhanced and supported through a multi-institutional consortium led by the Vanderbilt University CTSA.

11.2. Regulatory Considerations

All protocol amendments and consent form modifications will be made by the Principal Investigator. Should an external sponsor be identified, they will have the opportunity to review

and approve the changes prior to submission of these changes to the local IRB and distribution to participating sites.

12. STATISTICAL CONSIDERATIONS

12.1 Phase I Study Design/Endpoints

The phase I portion is a study of subjects with documented progressive metastatic CRPC with the primary endpoint of determination of MTD (or recommended phase II dose). In general, if there are sufficient numbers of subjects, descriptive statistics (e.g., number of observations, means, standard deviations, medians, and ranges) will be used to summarize data and selected endpoints may be summarized by dosing regimen. Otherwise, subject listings will be provided. No formal hypothesis testing is planned.

The dose-escalation schedule (using 3+3 modified Fibonacci escalation), definitions of DLT, and determination of MTD are defined above (Section 6.2.10). The design is constructed to reduce the chance of escalating the dose when the probability of DLT is high, and increase the chance of escalating the dose when the probability of DLT is low. The maximum tolerated dose is defined as the highest dose level with an observed incidence of DLT in no more than one out of six patients treated at a particular dose level. The dose escalation scheme provides the following probabilities of escalation based on the true chances of DLT at a specific dose level. One can see that the probability of escalation is high if the toxicity risks are low.

| | | | | | | | |
|------------------------------|------|------|------|------|------|------|------|
| True Probability of Toxicity | 0.05 | 0.10 | 0.20 | 0.30 | 0.40 | 0.50 | 0.60 |
| Probability of Escalation | 0.97 | 0.91 | 0.71 | 0.49 | 0.31 | 0.17 | 0.08 |

12.2. Phase II Study Design/Endpoints

We will enroll up to 27 subjects into the Phase II portion (including the 3-6 used for establishing the MTD). We will define evaluable patients as patients who met eligibility requirements, have initiated therapy, and were not removed from the study for non-compliance or patient withdrawal.

Sample size recommendations for the two-stage design are determined according to Simon's two-stage minimax design. We project a 30% PSA decline proportion of 35%, below which the regimen will be unacceptable and a 30% PSA decline proportion of 60%, above which the regimen will be considered worthy of further exploration. The null hypothesis that the 30% PSA decline proportion is less than or equal to 35% will be tested against the alternative hypothesis that the 30% PSA decline proportion is greater than or equal to 60%.

The sample size computations were performed assuming a 0.10 one-sided level of significance and 90% power assuming a historical control value for PSA decline of 35% and the alternative

hypothesis of 60%. If 6 or fewer of the first 16 evaluable patients do not experience a 30% decline in PSA (stage 1), the study will be terminated and declared to have a negative result. If 7 or more patients out of the first 16 evaluable patients experience a 30% decline in PSA, ongoing accrual will proceed to the target sample size of 27 patients (stage 2). The new regimen will be declared active in this patient population and worthy of further testing if 13 or more patients experience a 30% PSA decline among the 27 patients entered. This two-stage design yields a 0.90 probability of a positive result if the true 30% PSA decline proportion is 60%. It yields a 0.90 probability of a negative result if the true 30% PSA decline proportion is 35%. An exact 95% binomial confidence interval will be constructed for the proportion of patients with PSA decline.

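### The planned exact 95% interval for PSA decline is not aligned with the one-sided 0.10 two-stage test and takes no account of the stage 1 stop (minor)

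*Combined protocol and SAP*

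**What the plan says.** Section 12.2 sets up the phase II primary analysis as a Simon "two-stage minimax design". "The null hypothesis that the 30% PSA decline proportion is less than or equal to 35% will be tested" against an alternative of 60%, "assuming a 0.10 one-sided level of significance and 90% power". The stage 1 rule is: "If 7 or more patients out of the first 16 evaluable patients experience a 30% decline in PSA, ongoing accrual will proceed". With six or fewer responders among those 16 the trial stops and is called negative. At the end, the regimen is declared active if "13 or more patients experience a 30% PSA decline among the 27 patients entered".

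The section closes with its only statement about estimation: "An exact 95% binomial confidence interval will be constructed for the proportion of patients with PSA decline". It names no point estimator, does not say whether the interval allows for the stage 1 stop, and does not relate the 95% level to the one-sided 0.10 test. The efficacy analysis text under section 10.8 assigns binomial intervals to other endpoints, and section 12.5.2 treats PSA response descriptively, so neither settles the question.

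**The concern.** Two features of the interval do not match the test.

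- **Level.** A two-sided 95% interval puts 0.025 in each tail, whereas the test allows 0.10 in one tail. Some results will pass the test while the interval still contains the null rate of 35%.
- **Sampling plan.** An ordinary exact binomial interval treats the final count as one fixed sample of 27. Trials with poor early results stop at 16, so the final count is not binomial with n = 27, and the sample proportion is biased.

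What is at stake is how the result is reported and read. This is the only interval planned for the phase II primary endpoint. A borderline positive trial would be published as active beside an interval that reaches below the rate the plan itself calls unacceptable, with nothing written in advance to explain why.

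**Working it through.** **Inputs, all from section 12.2.** Null rate 0.35; alternative 0.60; one-sided alpha 0.10; power 0.90; n1 = 16, continue at 7 or more; N = 27, success at 13 or more. Stage 2 therefore has 27 - 16 = 11 patients.

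**1. Reproduce the design.** With b(x; n, p) the binomial probability,

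P(positive | p) = sum over x1 = 7..16 of b(x1; 16, p) x P(X2 >= 13 - x1), where X2 ~ Bin(11, p).

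- p = 0.35: 0.0979, within the 0.10 limit.
- p = 0.60: 0.9001.

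A full search returns 6/16, 12/27 as the minimax design. The plan's figures are correct.

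**2. Intervals at the counts near the boundary.** The ordinary interval is Clopper-Pearson with n = 27. The two-stage interval uses stagewise ordering: its lower limit solves P(continue and total >= s | p) = a, and its upper limit solves P(stop at stage 1, or total <= s | p) = a. Here a = 0.025 for 95% and 0.10 for 80%.

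| Responders of 27 | Two-stage p at 35% | Ordinary 95% | Two-stage 95% | Ordinary 80% | Two-stage 80% |
|---|---|---|---|---|---|
| 13 (48.1%) | 0.0979 | 28.7-68.1% | 29.2-68.8% | 34.5-62.0% | 35.1-62.6% |
| 14 (51.9%) | 0.0508 | 31.9-71.3% | 32.2-71.5% | 38.0-65.5% | 38.2-65.7% |
| 15 (55.6%) | 0.0225 | 35.3-74.5% | 35.4-74.6% | 41.5-68.9% | 41.6-69.0% |

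At 13 and 14 both kinds of 95% interval include 35%; from 15 upward both exclude it. The two-stage 80% interval excludes 35% at every count of 13 or more. The ordinary 80% interval fails at 13 only, because the fixed-sample tail probability there is 0.111 against the design's 0.098.

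**3. How often the mismatch would appear.** P(total is 13 or 14, having continued), and its share of all positive results:

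- true rate 35%: 0.075 of 0.098, or 77%
- true rate 50%: 0.261 of 0.607, or 43%
- true rate 60%: 0.155 of 0.900, or 17%

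**4. Effect of ignoring the stage 1 stop.** Assume a stopped trial reports x1/16 and a completed one reports total/27.

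Bias(p) = sum over x1 <= 6 of b(x1; 16, p) x1/16 + sum over x1 >= 7 of b(x1; 16, p)(x1 + 11p)/27 - p.

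The largest bias is -2.0 points, near p = 0.41. At p = 0.60 it is -0.6 points.

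The UMVUE at a final total s is [sum of C(15, x1 - 1) C(11, s - x1)] / [sum of C(16, x1) C(11, s - x1)], over x1 from max(7, s - 11) to min(16, s):

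- 13: 50.7% against 48.1%
- 14: 53.2% against 51.9%
- 15: 56.1% against 55.6%
- 18 or more: no difference

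Coverage of the ordinary 95% interval under the design is 96.8% at p = 0.35 and 96.2% at p = 0.60. Its minimum over p from 0.05 to 0.95 is 94.4%, near p = 0.65. The stagewise 95% interval stays at or above 95% over the same range.

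**The case against.** The strongest reply is that nothing here is an error. The decision rests on the responder count; no text makes exclusion of 35% a condition of success. A one-sided 0.10 test and a two-sided 95% interval will disagree near the boundary in any design, single-stage included, and the plan states both levels openly. An interval reaching below 35% may even usefully warn that the evidence is borderline. Adjusting for the two stages moves the 95% lower limit by only about half a point at 13 (28.7% to 29.2%), against a width of about 39 points. The bias is downward, so it cannot overstate activity.

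Most of this stands. A reader might infer that the interval contradicts the decision rule, or that ignoring the two-stage design is what brings 35% inside it. The documents support neither. The rule never uses the interval, and the adjusted 95% intervals at 13 and 14 include 35% as well. The 77% share at a true rate of 35% is also conditional on a false positive; the unconditional probability is 0.075.

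Two things survive. The plan does not tell the reader that the two levels differ in meaning. And changing the level alone is not a complete remedy, since the ordinary 80% interval still includes 35% at 13 of 27.

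**Conclusion.** The point holds as a minor one about estimation and reporting. The test and its error rates are valid and need no change.

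The planned 95% interval is not aligned with the test at exactly two final counts, 13 and 14 of 27. At the 95% level that is wholly a mismatch of levels. Separately, leaving out the stage 1 stop biases the sample proportion low by up to 2.0 points and lets coverage fall marginally below nominal (about 94.4% at worst), so the interval is not strictly exact under this design. These are small defects, and the interval's performance is otherwise acceptable.

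The figures assume a total of 27 with 11 patients in stage 2, as section 12.2 implies. Sections 4.3 and 12.6 speak of 9 further patients, which does not add up to 27; that is a separate matter, and 27 is the total that reproduces the stated error rates. They also assume that the observed sample sizes are exactly 16 and 27, and that two-stage intervals use stagewise ordering.

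**What to change.** In section 12.2, replace the interval sentence with text that does four things:

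1. Makes the 95% interval a two-stage exact interval with stagewise ordering.
2. Reports the UMVUE beside the sample proportion.
3. Adds the stagewise two-sided 80% interval, or equivalently the one-sided 90% lower bound (35.1% at 13 of 27), as the interval that corresponds to the one-sided 0.10 test.
4. States that the 95% interval is for estimation and does not correspond to the decision rule.

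The cost is a short text change, a few lines of code and one more interval to report. Sample size, boundaries and patient procedures are untouched. Writing it down now also prevents the estimator and interval from being chosen after the count is known.
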